8.8 Safety Oversight

8.8.1 Data and Safety Monitoring Plan

The investigator will allocate adequate time for monitoring activities. The Investigator will also ensure that any compliance or quality assurance reviewers are given access to all the above noted study-related documents and study related facilities at UTHealth Houston if assigned. A detailed strategy outline can be found in the attached Data and Safety Monitoring Plan.

8.8.2 Data Safety Monitoring Board

Consistent with NIMH guidelines on data and safety monitoring, in advance of trial inception we will establish a DSMB. Details on DSMB role, composition, and operating procedures can be found in the attached Data and Safety Monitoring Plan. Clinical Monitoring. [name] will serve as Principal Investigator (PI) of the study. It is the responsibility of the PI to oversee the safety of the study at UTHealth Houston.

Imaging procedures will be conducted either at UTHealth Houston. The investigators for this project are not trained to perform radiological diagnosis, and the MRI scans performed in this study are not designed to find abnormalities and are being conducted only for research purposes. If the investigators notice a finding on an MRI scan that is of clinical significance and medically actionable, the scan will be shared with a licensed radiologist for further evaluation. Should this occur, a neuroradiologist would be consulted and the MRI scan will be sent to the UTHealth Houston. If the neuroradiologist thinks that further investigation of the finding is called for, the participant will be contacted about the finding and next steps. A copy of the radiology report will also be provided to the participant for their records. The decision as to whether to proceed with further examination or treatment lies solely with the participant and their physician. The images collected in this study do not comprise a proper clinical MRI study these images will not be made available for diagnostic purposes.

For this study, [name] and/or [name], licensed physicians, or a delegate (MD or NP) will be responsible for the prescription administration and all procedures related to the study treatments. All participants will be monitored for any adverse events related to Estrogen use and PE by an approved study physician, nurse practitioner, and psychologists involved in the study. A study Physician will be in charge of managing AEs, SAEs, and unanticipated problems related to study treatment and psychiatric risks to participants. The psychotherapy will be delivered by approved study clinicians but all medication related procedures will be overseen by IRB-approved, licensed MD or NP staff. [name] and [name] will work with the PI [name] to support all necessary reporting.

[name] serves as the overall PI of the proposal. He will oversee the implementation of fMRI-related tasks and aspects of the project and the fMRI data acquisition before and after treatment. [name] will monitor the safe implementation of the protocol at the center for brain imaging. [name] and/or [name] serve as the overseeing, licensed physician(s). They or their delegates will be responsible for the prescription administration and all procedures related to the study medication. The delegates will consult with [name]/[name] as needed/indicated. Clinical safety will be monitored by the psychologists, psychiatrists, and nurse, and all will consult with [name]/[name] as needed/indicated. The psychotherapy will be delivered by approved study clinicians but all medication related procedures will be overseen by IRB-approved, licensed MD or NP staff. The PI and study clinicians will meet as needed to discuss recruitment and retention, data acquisition and management and all matters related to the prescription and therapy. They will review any unanticipated emerging problems or serious adverse events in real time with each other or a delegated, responsible, licensed, IRB-approved medical clinician. The PI will be responsible for reporting to the IRB and DSMB.

9 Statistical Considerations

9.1 Statistical and Analytical Plans (SAP)

The data to be gathered from this study is multimodal: neurobiological responses (fMRI) before and after therapy, psychophysiological data obtained before, during, and after therapy, self-assessment questionnaires, and clinical data pertaining to PTSD symptoms ascertained before and after therapy. Our analytic approach will examine the impact of using estradiol as an adjunct to PE on all of these data. The major focus of the analytic approach will be to examine change in each of the above noted metrics before and after treatment and how the use of estradiol may have improved/changed these multimodal data.

9.2 Statistical Hypotheses

Hypothesis 1: Compared to the placebo-PE group (Plc+PE): 1) the E2+PE group will exhibit faster reduction of SCR between PE sessions, and 2) after 5 E2+PE sessions, the extinction recall deficit indexed by elevated SCR during extinction retention test will be rescued (i.e., SCR in the E2+PE group will be significantly lower

relative to the Plc+PE group). 2) Extinction-induced activations will be higher in the vmPFC and lower in the dACC and amygdala in post relative to pre E2+PE treatment. When comparing E2+PE vs. Plc+PE, similar differences are expected, but to a lesser degree given the anticipated benefits of PE alone.

Hypotheses 2: PTSD symptom severity will be significantly lower in the E+PE group relative to the Plc+PE group following treatment, as well as at the 3 and 6-month follow-up assessments.

Hypothesis 3: The degree of PTSD symptom reduction post- compared to pre-PE will be associated with BOLD changes in the fear extinction network and reduction in SCR during the extinction recall test after PE. The magnitude of BOLD and SCR changes will be significantly larger in the E2+PE group compared to the Plc+PE group.

9.3 Analysis Datasets

The proposed experiments in this project are aimed to examine the effects of E2+PE on the extinction-induced SCR and neural responses at post-PE sessions relative to pre-PE. SCR will be recorded as a psychophysiological index of fear extinction and extinction recall. We will conduct standard fMRI analyses to examine information flow changes in the extinction network. These data will test hypothesis 1 stated above.

Another objective of the project is to examine the impact of E2 administration on PE efficacy at reducing PTSD symptom severity. Here, we will use all clinical data (CAPS) before and after treatment as well as 3, 6 months follow up data. These data will be used to test hypothesis 2 stated above.

The combined data sets will then be used to test hypothesis 3 above.

Primary analyses will be based on a modified intent to treat sample including all participants who took at least one dose of the study medication.

9.4 Description of Statistical Methods

9.4.1 General Approach

Statistical Methods

SCR Analyses

For all experimental phase, SCR will be computed for each trial by subtracting the mean skin conductance level observed during the last two seconds of context presentation from the maximal skin conductance level reached during CS presentation. All SCR values will be square-root transformed prior to any statistical analyses. To evaluate extinction recall, an extinction retention index (ERI) will be computed for each individual using the following formula: $100 - (\text{mean SCR to the first 4 CS+E trials during recall} / \text{maximum SCR reached during conditioning for this same cue}) * 100$.

Functional MRI analysis

The specific emphasis of the fMRI analysis will be on the extinction recall phase (first four trials of the CS+E vs. first four trials of the CS+U contrast). This contrast has been chosen given the literature demonstrating a significant deficit of PTSD patients during that specific phase of the experimental protocol. BOLD signal will be extracted from the four ROIs (amygdala, dACC, vmPFC and hippocampus). For each of these ROIs, we will use mixed model ANOVAs with time (pre vs. post PE) and group (E2+PE vs. Plc+PE) to investigate main effect of each of these variables as well as group by time interaction. Whole-brain analyses will also be conducted as supplemental analyses for the sake of completeness. We will also conduct regression analyses comparing the change in BOLD responses in each of our ROIs from post- to pre-treatment with PTSD symptom reduction in each of the two groups (E2+PE and Plc+PE).

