Population	Sample size is 80 enrolled subjects, 40 at UTHealth Houston, 40 at Penn. Participants will be females ages 18-45 with chronic (at least 1 month post-trauma) DSM-5 FULL PTSD diagnosis and a Clinician-Administered PTSD Scale for DSM-5 (CAPS) Past Month version score ≥ 20 OR chronic (at least 1 month post-trauma) subPTSD diagnosis and CAPS Past Month version score of ≥ 20 (subPTSD defined as: meeting criterion A, F, G, H, and clusters B, C, and at least 1 of the clusters D or E.). Trauma needs to fall under Criterion A. Participants will be on stable medications (for 3 or more months by the time of study entrance), outpatient, and will provide informed consent. For naturally cycling female subjects, stage of menstrual cycle will be ascertained by history, and by serological measures. For women on oral contraceptives, we will identify those using monophasic or biphasic of first, second, third or fourth generation with up to 35mcg of ethinyl estradiol.

Study Sites	UTHealth Houston [REDACTED]
	[REDACTED] University of Pennsylvania Perelman School of Medicine
	[REDACTED]
Number of participants	80 participants expected to be enrolled across 2 sites
Description of Study Agent/Procedure	Study drug will consist of one 2.0 mg dose of estradiol, (obtained from Estrace® Tablets, 2.0 mg estradiol tablets, USP, Warner Chilcott [now Allergan, as Warner Chilcott was acquired by Allergan]) taken orally.
Reference Therapy	Placebo
Key Procedures	Pregnancy Test, Urine Toxicology Screen, fMRI scan, Blood Draw, Estradiol/Placebo Dosage
Statistical Analysis	For all aims, analyses of SCR will test for group x condition interactions for the different groups in each aim with respect to CS+E vs. CS+U. With respect to the fMRI data, the initial analysis will involve assessing for a main effect of group (E vs. Plc), post treatment using CS+E vs. CS+U contrast. In addition, we will compare post treatment brain activations vs. pre-treatment within each group as well as the interactions between time and group also using the same imaging contrast.

Schematic of Study Design

Process Diagram

Visit 0: Telephone Screening

- Local advertising efforts instruct prospective participants to complete a screener
- The Research Assistant/study team member at UTHealth Houston calls and screens individuals for eligibility based off of the screener. Such screening is routine at UTHealth Houston and requires about 30 minutes.

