9.5 Sample Size

Pre to post treatment assessment using our experimental approach has not been previously conducted, and therefore it is challenging to calculate power to estimate potential sample or effect size comparing the pre to post time-points. The following sample size calculations pertain to the expected changes related the psychophysiological and neurobiological indices to be obtained. The sample size selected for this proposal is based on the detection of between-group significant differences at an alpha of .05 using data collected in our previous study of fear conditioning and extinction recall in controls and patients (PTSD) and using our preliminary fMRI data in women with high (HE) vs. low estradiol (LE) (Zeidan et al, 2011). We have calculated our power to detect between-group differences with a sample size of 25 subjects per group. Based on our previous experience with this population and this paradigm, we expect that (at each of the two time points) it is possible that we will have unusable data in approximately 20% of the subjects due to data of insufficient quality for at least one phase of the experiment. Reasons for this include poor SCR responses, head motion during scanning, or technical difficulties with SCR or fMRI. In addition, we anticipate dropout of ~20 % of patients after the initiation of the study. Thus out of the total of 80 patients, we expect to obtain a full data set (from all time points) from 50 patients. By using the effect size obtained from our previous study (see above), an alpha level of 0.05 and 50 patients, we will have 85% power to detect a significant between-group difference. Regarding the clinical measures, we do not have data to calculate power because of the novelty, but since it is a preliminary proof-of-concept aim, the results to be obtained will help inform future power analyses and calculations for this line of research.

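### The primary sample is all dosed participants, but the plan does not say how a dosed participant with one unusable recall session enters the BOLD or SCR analysis; a mixed model on every usable visit would keep her data and gain power

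*Combined protocol and SAP*

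**What the plan says.** Section 9.3 fixes the analysis set: "Primary analyses will be based on a modified intent to treat sample including all participants who took at least one dose of the study medication". Section 6.1.7 repeats it. Section 4.2.1 makes recall BOLD and SCR the primary endpoint.

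For BOLD in the four regions of interest, section 9.4.1 says: "For each of these ROIs, we will use mixed model ANOVAs with time (pre vs. post PE) and group (E2+PE vs. Plc+PE". It has no rule for a participant whose scan is usable at only one of the two time points.

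For SCR, section 9.4.1 defines a derived variable ("To evaluate extinction recall, an extinction retention index (ERI) will be computed for each individual using the following formula") and stops there. The Statistical Analysis row of the Protocol Summary adds only that "analyses of SCR will test for group x condition interactions for the different groups in each aim". The same row gives, for fMRI, a comparison that needs no pre-treatment scan: "the initial analysis will involve assessing for a main effect of group (E vs. Plc), post treatment using CS+E vs. CS+U contrast".

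Section 9.4.6, under Baseline Descriptive Statistics, plans GEE and linear mixed models for intent-to-treat and completer analyses, with missing-data sensitivity analyses. It motivates them by a schedule of baseline, post-treatment and two follow-ups. Section 7.1.2 states that follow-up includes no conditioning experiment and no fMRI.

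Section 9.5 expects "unusable data in approximately 20% of the subjects due to data of insufficient quality for at least one phase of the experiment", applied at each of the two time points, plus about 20% dropout, and concludes: "Thus out of the total of 80 patients, we expect to obtain a full data set (from all time points) from 50 patients". Section 9.4.2, on the primary endpoint, refers to sections 10.1 to 10.3, which hold no analyses.

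**The concern.** The promised sample and the named model do not fit together without a further rule. A two-time-point mixed ANOVA in its classical split-plot form needs both measurements. A dosed participant with a good Visit 11 scan and a failed Visit 3 scan would leave the analysis, although she carries direct information on the arm difference after treatment. The result would then describe those who gave clean data twice, not those who took a dose.

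Nothing elsewhere clearly settles the matter. Section 9.4.6 offers suitable models, but on a visit schedule that BOLD and SCR do not follow. Section 9.4.1 names a different method for BOLD and none for SCR. Under section 9.4.9 the analyses follow unblinding, so the choice between complete pairs and all usable data could be made with the results in view.

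**Working it through.** **Inputs.** From 9.5: 80 patients, 20% dropout, 20% unusable data, 25 per group, alpha 0.05, power 85%. No effect size or pre-post correlation is printed. Assumed here: all 80 dosed, losses independent, equal arms, two-sided test, unit SD, correlation ρ of 0.3 to 0.7.

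**The plan's figure.** Applying the 20% data loss once gives 80 × 0.8 × 0.8 = 51.2; adding the two losses gives 80 × 0.6 = 48. Either matches 50. Applying the loss at each time point, as worded, gives 80 × 0.8³ = 41.0, which does not.

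**Who has what.**
- (A) 20% unusable at each visit. Both: 41.0. Post only: 80 × 0.2 × 0.8 × 0.8 = 10.2. Pre only: 80 × 0.8 − 41.0 = 23.0. Neither: 5.8.
- (B) 20% lost once, spread evenly over the visits: (1 − u)² = 0.8, so u = 0.106. Both: 51.2. Post only: 80 × 0.106 × 0.8 × 0.894 = 6.0. Pre only: 80 × 0.894 − 51.2 = 20.4. Neither: 2.4.

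**Variance of the arm effect**, with b pairs and p post-only participants per arm:
- paired time × group interaction: 4(1 − ρ)/b
- baseline-adjusted pairs (ANCOVA): 2(1 − ρ²)/b
- mixed model with a common baseline mean, all usable visits: 2/[b/(1 − ρ²) + p]

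The number of pre-only participants does not appear in the last formula. With equal arms they add nothing to the Visit 11 arm difference; a numerical least-squares check with and without them gave the same variance.

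**Power** = Φ(d/√variance − 1.96). Example for (A), ρ = 0.5, d = 0.6, b = 20.48, p = 5.12:
- interaction: 2/20.48 = 0.0977; Φ(1.92 − 1.96) = 48%
- ANCOVA: 1.5/20.48 = 0.0732; Φ(2.22 − 1.96) = 60%
- constrained model: 2/(27.31 + 5.12) = 0.0617; Φ(2.42 − 1.96) = 68%

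The second effect size, d = 0.865, is what 85% power with 25 per group implies under a two-sided t test.

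| d | ρ | (A) interaction / ANCOVA / constrained | (B) interaction / ANCOVA / constrained |
|---|---|---|---|
| 0.6 | 0.3 | 37 / 52 / 61% | 44 / 61 / 66% |
| 0.6 | 0.5 | 48 / 60 / 68% | 57 / 70 / 73% |
| 0.6 | 0.7 | 70 / 77 / 81% | 79 / 85 / 87% |
| 0.865 | 0.3 | 65 / 83 / 90% | 74 / 90 / 93% |
| 0.865 | 0.5 | 79 / 89 / 94% | 87 / 95 / 96% |
| 0.865 | 0.7 | 95 / 97 / 98% | 98 / 99 / 99% |

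These are large-sample values. Simulation of (A) at ρ = 0.5 (2,500 trials per setting) gave slightly lower figures for ANCOVA and the constrained model: 57% and 67% at d = 0.6, and 86% and 92% at d = 0.865. Type I error was 5–6% for both.

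The step from ANCOVA to the constrained model is the gain from the recovered data: 1 to 9 points in (A), 0 to 5 in (B). The step from the interaction test also includes the gain from using baseline well: 3 to 25 points in (A), 1 to 22 in (B).

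**The case against.** A reader might infer that the plan prescribes a completer analysis and discards usable data. The documents do not support that.

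- The 50 full data sets in 9.5 are a sample-size forecast, not an exclusion rule. The pooled loss for failure in any phase is also a planning allowance. No text says that failed SCR removes a participant from the BOLD analysis, or the reverse.
- The ANOVA is assigned to BOLD regions only, so the criticism of a two-time-point ANOVA does not reach SCR. There the gap is the lack of a stated model.
- The Protocol Summary's initial fMRI comparison is post-treatment only and would keep a participant with no usable Visit 3 scan. However, 9.4.1 does not carry that test forward, and Hypothesis 1.1 in section 3.1 rests on the Time × Group interaction.
- A mixed model can be fitted to incomplete pairs, and 9.4.6 never restricts its methods to the clinical scale. Both readings are possible; neither is stated.

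It is also tempting to say that 74 participants (41 + 10 + 23) would be used instead of 41. That overstates the gain, because the 23 pre-only participants add nothing to the proposed arm difference. Some of them may also have left before the first dose and so fall outside the analysis set.

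Finally, at d = 0.865 and ρ = 0.5, baseline-adjusted pairs already reach 89% with 41 pairs, above the plan's 85%. The case for change is efficiency and clarity, not a trial that fails without it.

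**Conclusion.** The point holds as a gap with a better method available. The all-dosed sample in 9.3 is not reconciled with the BOLD model in 9.4.1, SCR has no inferential model there, and no missing-session rule is clearly tied to either signal. The plan neither imposes nor prevents a complete-pair analysis.

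The gain is real but modest for the recovered data alone, and larger against the interaction test as named, mainly because the constrained model also uses baseline more efficiently. All power figures rest on an assumed effect size, correlation and independent losses. The participant counts also assume that all 80 are dosed. The power figures are less sensitive to that, because patients who leave before the first dose have no post-treatment session. Severity: cheap improvement, not must-fix.

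**What to change.** In 9.4.1, state that recall SCR and each BOLD region are analysed with a likelihood-based linear mixed model using every usable visit from every dosed participant. Constrain the baseline mean to be equal between arms; this is reasonable because section 7 places randomisation after Visit 3. The time × group term is then the Visit 11 arm difference, so the interaction in Hypothesis 1.1 is still what is tested. Judge usability separately for SCR and for each scan. Report the complete-pair ANOVA as a sensitivity analysis. Say which methods in 9.4.6 apply to SCR and BOLD, and correct the references in 9.4.2.

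The cost is SAP wording and a standard model, with no new data. The downside is that the model relies on data being missing at random given the observed visit, which the missing-data sensitivity analyses in 9.4.6 could be extended to examine.

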3.1 Primary Objective

The primary objective is to delineate the influence of exogenous administration of estrogen on conditioned responses during extinction recall in women with PTSD.

Specific Aim 1.1: To examine the effects of E2+PE on the extinction-induced psychophysiological responses (SCR), neural responses, and the information flow between the fear extinction nodes at post-PE sessions relative to pre-PE.

Hypothesis 1.1: During extinction recall, both groups will show lower SCR at post- relative to pre-PE. A general improvement is expected over time in both groups given the anticipated benefits of PE alone. However, we expect a significant Time x Group interaction, where the Estradiol-treated group should exhibit significantly lower fear levels (indexed via SCR) at the follow-up assessment relative to the Placebo group. 2) For both groups, extinction recall-induced activations will be higher in brain regions associated with extinction learning and recall (i.e. vmPFC and hippocampus) and lower in regions associated with fear expression (i.e. dACC and amygdala) at post- relative to pre-treatment. Note that a general improvement from pre to post is expected in both groups, given the anticipated benefits of PE alone. We do expect, however, a significant

Time x Group interaction, with most pronounced effects at post-PE in the estradiol-treated group. 3) Information flow between the extinction nodes will improve (indexed by DCM models), with stronger effects in E2+PE after treatment.

Specific Aim 2: To examine the impact of E2 administration on PE efficacy at reducing PTSD symptom severity.

Hypothesis 2: PTSD symptom severity will be significantly lower in the E2+PE group relative to the Placebo+PE group following acute treatment, as well as at the 3- and 6-month follow-up assessments.

Specific Aim 3: To test the interaction between E2+PE induced psychophysiological and neuronal changes (pre-to-post) with the improvement of PTSD symptom severity.

Hypothesis 3: PTSD symptom reduction will correlate with BOLD and SCR changes observed during extinction recall following PE.

4 Study Design and Endpoints

Section 4 will provide a brief overview of the phases of the clinical protocol (screening, baseline, experimental days). More details on procedures occurring during each phase will be included in subsequent sections of the protocol.

Therapist Training Procedures:

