9.4.2 Analysis of the Primary Efficacy Endpoint(s)

Details of the analyses for the primary efficacy endpoints are provided above in sections 10.1, 10.2, and 10.3.

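### No primary BOLD treatment test is named, and no planned model adjusts for the pre-treatment scan or the severity stratum

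*Combined protocol and SAP*

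**What the plan says.** BOLD signal during recall is a primary endpoint, together with SCR (section 4.2.1). Its treatment test is described in several places.

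- **Protocol Summary, Statistical Analysis:** "the initial analysis will involve assessing for a main effect of group (E vs. Plc), post treatment using CS+E vs. CS+U contrast". Within-group pre-post comparisons and the time-by-group interaction are then added.
- **Section 3.1, Hypothesis 1.1:** the expected arm difference is a "Time x Group interaction, with most pronounced effects at post-PE in the estradiol-treated group".
- **Section 9.1:** "The major focus of the analytic approach will be to examine change in each of the above noted metrics before and after treatment".
- **Section 9.2:** Hypothesis 1 begins with a within-arm statement, "Extinction-induced activations will be higher in the vmPFC and lower in the dACC and amygdala in post relative to pre E2+PE treatment". Hypothesis 3 expects larger BOLD and SCR changes with estradiol than with placebo, which is an arm difference in change.
- **Section 9.4.1:** for each of four regions, "we will use mixed model ANOVAs with time (pre vs. post PE) and group (E2+PE vs. Plc+PE) to investigate main effect", followed by the interaction, with no ranking.
- **Section 9.4.2:** "Details of the analyses for the primary efficacy endpoints are provided above in sections 10.1, 10.2, and 10.3". Section 10 concerns source documents and has no such subsections.
- **Section 9.5:** "we will have 85% power to detect a significant between-group difference", without an effect size or a named test. It also says that "it is challenging to calculate power to estimate potential sample or effect size comparing the pre to post time-points".

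Section 7.1.3 stratifies randomisation by baseline severity, and section 9.6.1 has CAPS severity entered to obtain the randomisation number. Neither the severity stratum nor the pre-treatment scan appears as a covariate in any BOLD model.

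**The concern.** The real choice is between the post-treatment comparison that the Protocol Summary puts first and the interaction towards which most of the other sections lean. They estimate the same treatment effect in a randomised trial, but with different precision, and which is better depends on a correlation that nobody yet knows. Section 9.4.9 places all analyses after the blind is broken. With no test designated, the primary BOLD result could rest on either, chosen once both are visible.

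A second issue is efficiency. Section 7 places randomisation after Visit 3, so the first scan is a true baseline. The post-only test ignores it, and the interaction uses it only by subtraction. Using it as a covariate would usually give a more precise estimate from data already collected.

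**Working it through.** **Inputs.** From section 9.5: alpha 0.05, 50 evaluable patients (25 per arm), 85% power. Not in the documents, hence assumed: a two-sided test, the effect size, the pre-post correlation r, and equal pre and post SDs (relaxed in step 4).

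**1. The plan's own figure.** The 85% cannot be reproduced because no effect size is stated; it can only be inverted. With 48 degrees of freedom the critical t is 2.011. A noncentrality of 3.058 gives 85% power, so d = 3.058 × √(2/25) = 0.865. This assigns the 85% to the post-only comparison, which is the simplest reading of a between-group difference but is still an assumption.

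**2. Formulas.** The treatment effect is d in each test, and the post-treatment variance is set to 1.

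- Post-only: variance factor 1.
- Interaction (difference in change): variance factor 2(1 − r).
- Baseline-adjusted: variance factor 1 − r², with 47 degrees of freedom and a small penalty for chance baseline imbalance, averaged by simulation.

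Example at r = 0.3: the interaction has effective effect 0.865/√1.4 = 0.731, giving 71.7% power. The adjusted test has about 0.865/√0.91 = 0.907, giving 87.4% after the penalty.

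**3. Power with 25 per arm (%).**

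| r | Post-only | Interaction | Adjusted for pre-scan |
|---|---|---|---|
| 0 | 85.0 | 56.3 | 84.2 |
| 0.2 | 85.0 | 65.9 | 85.6 |
| 0.3 | 85.0 | 71.7 | 87.4 |
| 0.5 | 85.0 | 85.0 | 92.8 |
| 0.7 | 85.0 | 97.2 | 98.6 |

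The adjusted test breaks even with post-only near r = 0.15. Adding a two-level stratum with no true effect, balanced by design, gives 83.8, 85.6, 87.5, 92.6 and 98.5% in 20,000 simulated trials, so the extra term costs almost nothing. The ordering is the same for other effect sizes. At r = 0.3, adjusted, post-only and interaction power are 43.5, 41.0 and 31.0% for d = 0.5, and 82.0, 79.1 and 64.9% for d = 0.8.

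**4. Unequal SDs.** If the pre SD is k times the post SD, the interaction's variance factor is 1 + k² − 2rk; adjusted power does not change.

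- k = 1.25, r = 0.3: factor 1 + 1.5625 − 0.75 = 1.8125, interaction power 60%.
- k = 0.8, r = 0.3: factor 1 + 0.64 − 0.48 = 1.16, interaction power 80%.
- k = 0.8, r = 0.7: factor 1 + 0.64 − 1.12 = 0.52, interaction power 98.6%, a tie with the adjusted test.
- k = 0.5, r = 0.5: factor 1 + 0.25 − 0.5 = 0.75, about 93% for both.

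**5. Missing pre-scans.** With 50 usable post-scans and an assumed 20% of pre-values missing at random, mean imputation plus an indicator gives 84.7, 86.1, 90.6 and 96.6% at r = 0.2, 0.3, 0.5 and 0.7. Most of the gain survives.

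**The case against.** The strongest reply is that the interaction is already the implied primary test. It appears in the Protocol Summary, in section 3.1 and in section 9.4.1, and it matches section 9.1 and Hypothesis 3 in section 9.2. That is a fair account of where the plan leans. It does not settle the matter: the Protocol Summary puts another test first, section 9.4.2 points nowhere useful, and section 9.5 describes pre-to-post power as hard to calculate. If the interaction is primary, its power is not stated.

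A reader might infer three rival treatment tests, the third being the group main effect averaged over both scans, with 46% power at r = 0.3. The documents do not support that. Section 9.4.1 lists it as a routine ANOVA term, and no hypothesis is attached to it.

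A reader might also infer that the adjusted test always beats the interaction, or that the trial is underpowered because the interaction falls below 85% when r is under 0.5 with equal SDs. The first fails when the pre SD is smaller than the post SD (step 4). The second needs a value of r that the documents do not give.

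It is also fair to say that no power gain from the stratum can be shown. No severity-BOLD correlation is given, and section 7.1.3 states neither cut-points nor the number of levels. The stratum belongs in the model because randomisation was stratified on it.

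**Conclusion.** The point holds as one of pre-specification and efficiency. The time-by-group ANOVA is a valid analysis. The absence of a designated primary BOLD test is a fact of the text and needs no assumption about r or d.

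The size of the efficiency gain does depend on assumptions: d = 0.865, 25 per arm, two-sided 0.05, approximate normality, and an unknown r. With equal SDs, the adjusted test gains about 20 points over the interaction at r = 0.2, 16 at r = 0.3, 8 at r = 0.5 and 1 at r = 0.7. Over post-only it gains about 2 points at r = 0.3, 8 at r = 0.5 and 13 to 14 at r = 0.7. It loses about 1 point at r = 0. Its merit is that it stays close to the better of the other two tests, or above it, without knowing r in advance. These figures are for BOLD and should not be carried over to SCR.

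**What to change.** 1. In section 9.4.1, name one primary BOLD treatment test for each region: the arm coefficient from a regression of the post-treatment value on arm, pre-treatment value and the CAPS severity stratum as defined in the randomisation table. Label the interaction, the main effects and the within-group contrasts as supportive.
2. State one method that keeps participants without a usable pre-scan, for example mean imputation plus an indicator, or a constrained-baseline mixed model. Apply the missingness sensitivity analyses of section 9.4.6 to missing post-scans.
3. Use the same form for SCR once the plan says which recall measure is primary: the retention index of section 9.4.1 or the CS+E versus CS+U comparison of the Protocol Summary.
4. Align the Protocol Summary, section 3.1 and section 9.4.2 with the named test. In section 9.5, give the effect size and the test to which the 85% applies.

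How the four regions and SCR combine is a separate question for section 9.4.10.

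The cost is wording, plus stating the stratum definition. No new data are needed. The statistical price is about 1 point of power against post-only if r is near zero.
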